#### Infant growth:

Anthropometric measures including weight, length and head circumference will be measured at birth and monthly until study completion (4 months of age) using standardized procedures including length boards and non-stretchable tape measures for in person visits. For virtual visits, parents will be provided with tape measures at the time of birth as well as information from the SickKids "About Kids Health" website on how to measure their infant's weight and length at home (21). This information is available in print format in multiple languages as well as in audio and video files. These instructions have already been successfully implemented in virtual clinics at SickKids Hospital. Additional information will be provided on measuring the head circumference. Study staff will provide further guidance during virtual visits. In the event that there is an observed decline in growth during any of the follow-up visits (at 1, 2, 3, and 4 months old), as indicated by z-score data aligned with WHO growth standards for weight, length, or head circumference, the following procedures will be implemented: If parents or caregivers are responsible for taking these measurements and have expressed concerns regarding their child's growth, we acknowledge that these concerns may stem from imprecise measurements or possible errors. In such instances, it will be requested that parents or caregivers consult their healthcare provider to verify the measurements and address any potential issues. Comprehensive information and guidance will be offered to facilitate this follow-up, ensuring that any concerns are rigorously assessed and appropriately managed by a qualified healthcare professional.

#### Infant health and temperament (Infant Behavior Questionnaire):

Parents will be asked to report on a variety of health indicators for their infant at each time-point post hospital discharge including rehospitalization, visits to physicians (virtual or in person), emergency rooms, walk-in clinics or allied health professionals (including lactation consultation) and prescription and non-prescription medication use. It is anticipated that all of these health indicators will be ameliorated with the duration of exclusive human milk feeding. Infant

temperament will be assessed at 1-, 2-, 3- and 4-months with the Infant Behavior Questionnaire- Revised, Very Short Form which is a survey of 37 items spanning 3 broad scales including negative emotionality, positive affectivity, and orienting/ regulatory capacity (22). Our hypothesis is that infant temperament can reciprocally impact human milk feeding outcomes (e.g., a baby with colic may be more likely to receive formula supplementation whereas the use of formula may also impact the baby's temperament).

#### Breastfeeding self-efficacy (Breastfeeding Self-Efficacy Scale):

This will be administered at each time-point post hospital discharge to assess the trajectory of feeding practices. A parent's perception of their ability to breastfeed has been shown to predict both duration and exclusivity of breastfeeding (23). A tool to measure this perception has been developed by Dennis et al. and validated in Canada. This has been updated to a shortened version (Breastfeeding Self-Efficacy Scale – Short Form, BSES-SF) which consists of 14 items scored on a 5-point Likert scale ranging from not at all confident to always confident (24). Understanding parent's feeding self-efficacy provides important context to the duration and exclusivity of human milk feeding as well as infant growth throughout early infancy; it is possible that low breastfeeding self-efficacy may confound exclusive human milk feeding at 4 months of age. Further these outcomes may illustrate areas for intervention to support the duration and exclusivity of human milk feeding and growth among infants admitted to a well-baby unit following birth.

#### Parental stress, anxiety and depression:

Very little is known about the relationship between donor milk and parental mental health; this has been highlighted as an area requiring further study (25). Two well-established self-reported assessment tools will be employed to measure parental mental health at 2 and 4 months CA. For families with two parents, both will be asked to independently complete the same questionnaires. Anxiety will be measured with State-Trait Anxiety Inventory (STAI) which has been used to assess trait (20 items) and state (20 items) anxiety. This tool has been validated in different populations including postpartum women (26). STAI has been used to differentiate anxiety from depressive syndromes and to generally assess caregiver distress in research (27). The Edinburgh Postnatal Depression Scale (EPDS) has been classically described for screening for postpartum depression in mothers using a 10-point scale. There is evidence for its validity in fathers and therefore all parents will be invited to complete this screening. The measurement of these outcomes will also allow us to explore how they may impact the duration and exclusivity of human milk feeding at 4 months.

If a participant fills out the survey through our online survey platform, REDCap, and their response to the EPDS suggests a high likelihood of depression or self-harm, we have a well-defined protocol in place to prioritize their safety. Within 24 hours of receiving such a response, our study team will be immediately notified. We will then promptly contact the participant, providing them with clear and detailed instructions on how to access the necessary help and support. This may involve connecting them with a healthcare professional or emergency services as needed. If the survey is conducted via a phone conversation or in-person interaction, we will provide specialized guidance right away in the event of similar concerns.

#### Milk cortisol:

Milk cortisol is known to be associated with maternal distress and may play an important role in programming infant response to parental stress and may be related to infant growth (28, 29). Timed milk samples (morning sample to account for diurnal variation) will be collected at 2 and 4 months of age. These samples will be collected in the morning, within two hours after waking up, to account for the natural rise in cortisol levels during this time. We aim to collect these samples preferably between 6:30 AM and 8:30 AM. This timing consistency aligns with the screening tool for parental stress, anxiety, and depression questionnaires, which will also be administered at similar time points. Cortisol concentrations will be guantified using an enzymelinked immunosorbent (ELISA) assay or liquid chromatography-tandem mass spectrometry (LC-MS/MS) in [name] [name]'s laboratory at the University of Toronto In order to facilitate the milk sample collection process for our participants, we will ensure that special containers designed for this purpose are readily available to them. Our commitment to participant convenience and clarity extends to providing comprehensive instructions. These instructions will not only outline the precise methods and timing for collecting milk samples but will also specify the appropriate storage conditions, with an emphasis on keeping the samples stored in a -20°C freezer. Additionally, participants will receive guidance on the logistics of sending these samples to [name] [name]'s laboratory via courier. Furthermore, for those who opt for an inperson 4-month visit, the option to bring the samples with them will be made available, ensuring flexibility and ease in the participation process.

#### Economic evaluation:

In a recent systematic review, research was conducted on seven studies that compared the cost effectiveness of feeding infants with donor milk versus standard feeding in neonatal care. The studies were evaluated based on published full economic evaluations(30). In all 7 studies, the subjects were VLBW or low birth weight and donor milk interventions resulted in cost savings.

Our aim is to present a cost comparison between the two groups: the donor milk group and the formula group. We will collect medical expenses incurred by each infant during their initial hospital stay from the finance departments of the hospital. Direct costs will be evaluated based on the methodology presented by the Ontario Case Costing Initiative. Physician costs will be computed using the Ontario fee schedules. The cost of enteral feeds will be calculated by including the costs of both milk pump (if purchased or rented) and feeding formula or donor milk.

#### 1.8 Sample size estimation and power calculations

According to the systematic scoping review of McCune and Perrin published in January 2021, there are no data from RCTs comparing donor milk to formula for supplementation of late preterm or term newborns (13). The only available RCT is a pilot study that assessed the feasibility of using donor milk versus formula for a small group of 32 full-term and late preterm infants admitted to NICU; even though this study did assess certain aspects related to breastfeeding, such as feeding attempts and growth, the authors emphasized the need for larger-scale studies to validate the findings of this pilot study (15). The current exclusive breastfeeding rate in Toronto at 4 months of age is 28% (31). In one retrospective review following donor milk supplementation in late preterm and term newborns ( $\geq$ 35 weeks gestational age), the rate of exclusive breastfeeding rate to 56% would be clinically significant and plausible given the published data and was thus used for sample size calculation. With 80% power and an alpha level of 0.05, we require 47 infants in each of the two study arms. We anticipate, based on our prior work, a 15% loss to follow-up to 4 months of age (32); hence 56 infants will be recruited for each study arm or 112 infants in total.

#### 1.9 Analyses

#### 1.9.1 The proposed type of analyses:

Analyses will be carried out using SAS Version 9.4. Descriptive statistics will be calculated for all variables of interest. Unadjusted and adjusted models will be run to compare primary, secondary and exploratory outcomes. The primary outcome of exclusive human milk feeding will be compared between groups using a linear regression model. Secondary and exploratory outcomes will be assessed using linear and logistic regression models based on the nature of the outcome measure. The models will be adjusted for risk condition (being born to a diabetic mother or SGA) and sex. The primary analysis for this intent-to-treat study will include all infants as randomized, regardless of feeding protocol compliance.

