#### 1.6.1 Inclusion criteria:

Infants admitted to the well-baby unit at Sinai Health whose parent(s) intend to feed parent milk and who require supplementation:

- Infants of gestational/ type 1/ type 2 diabetic mothers
- Infants who are born small for gestational age (SGA) by using a sex-specific reference population and determining if their birth weight falls below the 10th percentile for gestational age
- Infants with a birth weight less than 2.5 kg

Note: Families will be approached according to the above stated criteria however only registered for trial participation if consent is secured and the infant require supplementation.

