#### 1.6.4 Practical arrangements for allocating participants to trial groups

Families will be invited to participate in the trial during their antenatal visits to the diabetes and placenta clinics. If they agree to participate, they will be asked to sign the consent form. After giving birth, upon admission to the well-baby unit they will be approached again for confirmation of their willingness to participate in the trial and to add infant's name to the consent form. Infants who are prescribed a supplement will be entered into the trial and randomly assigned to either the donor milk or formula group. Prior to the start of the study, a unique randomization schedule will be generated. The computer-generated randomization schedule will be securely stored in a sealed binder, with each participant's allocation placed in separate envelopes. These envelopes will be securely held in a locked procedure room, either within the well-baby unit. Importantly, to maintain blinding, the study coordinator will access the randomization schedule one envelope at a time during participant enrollment and allocation. This approach ensures that the study coordinator cannot see whether a participant will receive donor milk or formula until the point of assignment. The study allocation will be randomly assigned in a 1:1 ratio, using random blocks of 2 or 4. Furthermore, to prevent potential bias and uphold the integrity of the randomization process, the randomization schedule will incorporate stratification factors. These factors include whether the infant was born to a diabetic mother, whether they are small for gestational age, and the infant's sex. Stratification will facilitate the equitable distribution of supplementation rates across these distinct groups, thereby contributing to the robustness of the randomization process.

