#### 1.6.5. Communication of group allocation with the nursing staff and parent(s):

The responsibility for communicating group allocation lies with the study coordinator. Following the completion of the randomization process, parents and nursing staff will be informed of the group allocation, as the study is open-label, and this information aligns with the study design. During this discussion, parents will receive a clear explanation of their infants' group assignment, including its implications and details regarding the associated supplementation. It will also emphasize the voluntary nature of participation and the option for parents to withdraw from the study at any point.

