#### Infant Feeding Intentions:

At baseline, the Infant Feeding Intentions (IFI) scale (19) will be employed to quantitatively measure the intensity of mothers' intentions to commence breastfeeding and sustain it as the exclusive source of nourishment for their infants for the recommended duration of 6 months, as advocated by public health agencies. The IFI scale is a valid and simple tool comprised of five carefully constructed questions designed to capture the essence of these intentions accurately.

The initial two items of the scale focus specifically on assessing the strength of intention to initiate breastfeeding, offering valuable insights into the mother's commitment from the outset. Subsequently, the remaining items of the scale examine the intensity of intention to exclusively breastfeed at distinct milestones: 1 month, 3 months, and 6 months of age.

By utilizing the IFI scale, our study aims to obtain a precise and quantitative understanding of the degree of intention and dedication displayed by mothers towards initiating and maintaining breastfeeding. This comprehensive evaluation will provide valuable insights into the dynamics of infant feeding practices, enabling the development of effective strategies and interventions to support and encourage breastfeeding.

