#### Table 2: Study Timeline

Task	2023 Apr-Jun	2023 Jul-Sep	2023 Oct- Dec	2024 Jan- Mar	2024 Apr-Jun	2024 Jul-Sep	2024 Oct- Dec	2025 Jan- Mar
Trial preparation Protocol development Trial logistics development REB submission Training on outcome tools Staff in-servicing								
Trial management Patient recruitment Trial intervention Patients follow up Data collection								
Post trial completion Data analysis Manuscript preparation Knowledge translation								

Figure 1: Summary of study follow up and timing

In the case of multiple gestations (twins), each twin will be assigned to a different group, using a separate randomization plan with blocks of two, allowing for more precise comparisons and analysis. When two parents are available, both parents will be asked to separately complete the questionnaires.

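### The adjusted models leave out the baseline Infant Feeding Intentions score the trial already collects, which may forgo some precision on the primary outcome

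*Protocol*

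**What the plan says.** On the models, Protocol section 1.9.1 states "Unadjusted and adjusted models will be run to compare primary, secondary and exploratory outcomes" and then "The models will be adjusted for risk condition (being born to a diabetic mother or SGA) and sex". It does not say which of the two models is primary. The covariates correspond to the stratification factors in section 1.6.4: "These factors include whether the infant was born to a diabetic mother, whether they are small for gestational age, and the infant's sex".

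On the score, section 1.7 (Infant Feeding Intentions) states "At baseline, the Infant Feeding Intentions (IFI) scale (19) will be employed to quantitatively measure the intensity of mothers' intentions to commence breastfeeding". The first two of the five items concern starting to breastfeed, and "the remaining items of the scale examine the intensity of intention to exclusively breastfeed at distinct milestones: 1 month, 3 months, and 6 months". The purpose given is descriptive, namely to understand mothers' intentions. Neither the models in 1.9.1 nor the subgroups in 1.9.3 use the score.

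**The concern.** The primary outcome is exclusive human milk feeding at 4 months. Three of the five IFI items ask about intention to breastfeed exclusively at ages on either side of that point. A baseline measure so close in content to the endpoint is a natural candidate to explain outcome variance, and adjusting for a prognostic baseline variable narrows the confidence interval without recruiting more infants.

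The protocol is not silent on covariates. It states a set, and that set omits this one. The trial is also open label, so a covariate of this kind is best fixed before data are seen. What is at stake is precision only. Randomisation keeps the estimate valid with or without IFI.

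**Working it through.** **Inputs from the protocol (section 1.8).** Rates 28% and 56%; alpha 0.05 (sidedness not stated, two-sided assumed); power 80%; 47 evaluable per arm; 15% loss; 56 per arm and 112 in total recruited.

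**Reproducing the plan's figure.** The pooled-variance formula gives [1.96·√(2·0.42·0.58) + 0.842·√(0.28·0.72 + 0.56·0.44)]² / 0.28² = 47.6, so 48 per arm. The arcsine formula gives 47.3. Power at 47 per arm is 79.5%. Then 47/0.85 = 55.3, so 56 per arm and 112 in total. The sample size stands and does not rely on covariates.

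**Simple variance formula.** SE of the risk difference = √[(0.2016 + 0.2464)/47 · (1 − R²)], where R² is the share of within-arm outcome variance that IFI explains. The protocol gives no value, so R² is assumed over a range.

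- R² = 0: SE 0.0976, half-width 1.96 × 0.0976 = 19.1 points.
- R² = 0.05, 0.10, 0.20: half-width 18.7, 18.2, 17.1 points.
- Since 47 × (1 − R²) = 44.7, 42.3 and 37.6, about 45, 43 or 38 infants per arm with IFI match the precision of 47 without it.

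This ignores the cost of estimating one more coefficient, and it ignores twins.

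**Simulation.** 20,000 trials per setting, 47 per arm. IFI is standard normal per mother, with logistic slopes 0 / 0.3 / 0.5 / 0.75 / 1.2, giving R² of about 0 / 0.02 / 0.05 / 0.10 / 0.20. The linear model has treatment, diabetes, SGA and sex (assumed prevalences 60%, 40%, 50%, not prognostic), with and without IFI. Robust standard errors are clustered by mother.

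Twins matter because, in the text after Figure 1 in section 1.11, "each twin will be assigned to a different group, using a separate randomization plan with blocks of two". Twins share one maternal score, so IFI explains nothing of the within-pair contrast. The number of pairs is not given; 0, 5 and 10 among 94 infants were assumed.

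| Assumed R² | 0 | 0.02 | 0.05 | 0.10 | 0.20 |
|---|---|---|---|---|---|
| Power (%) without → with IFI, no twins | 78.5 → 77.8 | 78.2 → 78.5 | 78.5 → 80.0 | 78.3 → 82.3 | 78.3 → 86.2 |
| Change in points, no twins | −0.7 | +0.3 | +1.5 | +4.0 | +7.9 |
| Change, 5 twin pairs | −0.7 | +0.1 | +1.4 | +3.4 | +7.2 |
| Change, 10 twin pairs | −0.3 | +0.1 | +1.6 | +3.0 | +6.4 |
| Half-width with IFI, no twins (19.7 without) | 19.8 | 19.6 | 19.3 | 18.8 | 17.7 |

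The SD of the estimate with IFI relative to without it, no twins, is 1.007 / 0.997 / 0.981 / 0.953 / 0.898. The extra coefficient therefore costs about 0.7% in SD when IFI is useless. Since 1.007² = 1.014, the break-even R² is near 0.01.

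A further run without twins (3,000 trials per setting) gave the same half-widths at R² of about 0, 0.05, 0.10 and 0.20, with power changes of −0.6, +1.8, +5.1 and +8.0 points.

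**Two sensitivities that lower the gain.**

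- *Shared mother effect.* With 10 twin pairs and a further mother effect (SD 1.5 on the logit scale), R² falls to about 0 / 0.01 / 0.03 / 0.06 / 0.12 and the power changes are −0.5 / −0.1 / +0.7 / +1.9 / +4.5 points.
- *Scores clustering high.* Section 1.6.1 admits infants "whose parent(s) intend to feed parent milk and who require supplementation". With half the scores piled at a ceiling and the same nonzero slopes, R² is about 0.006 / 0.02 / 0.04 / 0.07, and power rises by about 1 and 3 points at the two larger slopes.

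**The case against.** The strongest case against is that nothing here is wrong. The covariates match the stratification factors, which is coherent and valid, and further prognostic covariates are often left to the SAP, which is not at hand and may name IFI. That stands as far as it goes and is why the point is optional. It does not remove the point, because 1.9.1 does state a covariate list.

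Second, the size rests wholly on assumption, and even its sign depends on R². This also stands. The +7.9 points needs R² of 0.20 and no twins, and should not be read as typical.

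Third, eligibility may compress the scores. Restricting IFI to the upper half of the assumed normal distribution, or piling half the scores at a ceiling, puts three of the four nonzero slopes below R² of 0.05, where the gain is trivial. The real degree of restriction is unknown. The criterion concerns intention to feed parent milk and does not mention exclusivity or duration, which three IFI items measure, so useful variation may remain. The objection moves the case to the low end of the range above; it does not take it outside that range.

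Fourth, naming a primary model, clustering by mother and using robust errors for a binary outcome are separate matters that do not depend on IFI. That is correct. They are included below only because the covariate cannot be specified properly without them.

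Fifth, the protocol already says the scale is given at baseline, and 1.6.4 describes consent at antenatal visits. No text places IFI after allocation, so the timing sentence is a clarification.

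**Conclusion.** The point holds as an optional improvement of low severity. Section 1.9.1 names risk condition and sex, the IFI score is collected at baseline, and no section puts it in a model. The estimate stays unbiased and the sample size stands.

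The plausible result ranges from a loss of under one power point, if IFI predicts nothing, to a gain of 3 to 4 points at R² of 0.10 and 6 to 8 points at R² of 0.20, depending on the number of twin pairs. Below R² of about 0.05 the gain is negligible. These figures rest on the assumed R² and twin counts, on 28% versus 56% with 47 analysed per arm, and on a normally distributed score. Compressed scores or a strong shared mother effect would place the gain towards the lower end.

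**What to change.** In section 1.9.1, name the adjusted model as primary, with diabetes, SGA and sex as separate terms plus the continuous baseline IFI total. Report a risk difference with standard errors robust to the binary outcome and clustered by mother, and keep the unadjusted result as supportive. Replace missing IFI scores with the overall mean, ignoring arm.

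In section 1.7, state that the scale is completed before the allocation envelope is opened. Section 1.6.5 makes this necessary: after randomisation "parents and nursing staff will be informed of the group allocation, as the study is open-label", and stated intentions could shift once the arm is known.

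The cost is short additions to two sections, with no new instrument, visit or infant. The downsides are one extra coefficient (SE about 0.5% to 0.7% larger and power about 0.3 to 0.7 point lower if IFI predicts nothing), a missing-score rule and a timing requirement. The sponsor may reasonably decline, but should decide before outcome data are seen.

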#### 1.9.3 Planned subgroup analyses:

Subgroup analysis of primary and secondary outcomes will be according to risk condition (being born to a diabetic mother or SGA) and sex. The p-value for these analyses will be adjusted to account for multiple comparisons (Bonferroni adjustment).

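### The adjusted models name one composite risk term, while randomisation stratifies by diabetic mother and SGA separately: a small, avoidable loss of efficiency and an undefined covariate

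*Protocol*

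**What the plan says.** On randomisation, section 1.6.4 says: "These factors include whether the infant was born to a diabetic mother, whether they are small for gestational age, and the infant's sex". Allocation is 1:1 in blocks of 2 or 4.

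On eligibility, section 1.6.1 lists diabetic mother and SGA and adds a third route: "Infants with a birth weight less than 2.5 kg". The routes are not stated to be mutually exclusive.

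On analysis, section 1.9.1 says: "The models will be adjusted for risk condition (being born to a diabetic mother or SGA) and sex". The comparison is planned both with and without adjustment. The same section adds: "The primary analysis for this intent-to-treat study will include all infants as randomized".

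On subgroups, section 1.9.3 uses the same composite: "Subgroup analysis of primary and secondary outcomes will be according to risk condition (being born to a diabetic mother or SGA) and sex".

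The protocol nowhere gives the levels of the risk condition.

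**The concern.** Diabetic mother and SGA, as two yes/no factors, form four cells: diabetic only, SGA only, both, and neither. The last holds infants who enter only by weight under 2.5 kg. One two-level term cannot represent four cells, so the covariate as written does not match the factors that randomisation balances.

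If a model leaves out a balanced stratum that predicts the outcome, variation between strata stays in its residual. The standard error is then larger than the design warrants, the test is somewhat conservative, and some power is given away. The same covariate set serves the adjusted models for the primary, secondary and exploratory outcomes. The composite also defines the subgroups, where an infant with both conditions, or with neither, has to be placed somewhere.

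**Working it through.** **1. The plan's own figure.** Inputs from section 1.8: 28% versus 56%, 80% power, alpha 0.05 (taken as two-sided), 15% loss. With the pooled two-proportion formula,

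n = [1.96·√(2·0.42·0.58) + 0.8416·√(0.28·0.72 + 0.56·0.44)]² / 0.28² = (1.368 + 0.563)² / 0.0784 = 47.6 per arm.

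The protocol states 47. Then 47/0.85 = 55.3, hence 56 per arm and 112 in total. The sample size reproduces, and this point does not touch it.

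**2. What each coding does to the four cells.**

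| Cell | Either condition, yes/no | Diabetic versus SGA | Two separate terms |
|---|---|---|---|
| Diabetic only | yes | diabetic | yes / no |
| SGA only | yes | SGA | no / yes |
| Both | yes | no level | yes / yes |
| Neither (<2.5 kg only) | no | no level | no / no |

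**3. Is the either-condition term 'yes' for most infants?** Table 1 (2020) gives 501 infants of diabetic mothers, 74% supplemented, and 318 under 2.5 kg, 88% supplemented. That is 501 × 0.74 = 371 and 318 × 0.88 = 280. Even if none of the 280 had a diabetic mother or were SGA, 'yes' would cover at least 371/(371 + 280) = 57%. Every overlap and every heavier SGA infant raises that share. These are unit counts, not trial participants.

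**4. Hand calculation of the cost of either-condition coding.** Assumptions: 60% of infants have a diabetic mother, feeding rates differ by g between them and the others, balance within strata is exact, the composite term explains nothing, and there are 48 completers per arm. Between-stratum variance is g²·0.6·0.4, which is 0.0096 at g = 0.20 and 0.0216 at g = 0.30.

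- *No effect, 28% in both arms (variance 0.2016).* The standard error is too large by √[0.2016/(0.2016 − 0.0096)] = 1.025, or by √[0.2016/(0.2016 − 0.0216)] = 1.058. The effective critical value is 2.01 or 2.07, so the true test size is about 4.5% or 3.8%.
- *28% versus 56% (mean variance 0.224).* The composite model's standard error is √(2·0.224/48) = 0.0966. The true one is √(2·0.2144/48) = 0.0945 or √(2·0.2024/48) = 0.0918. Power with the composite is Φ[(0.28 − 1.96·0.0966)/0.0945] = 83.1% or, with 0.0918, 83.8%. With separate terms it is Φ(0.28/0.0945 − 1.96) = 84.2% or, with 0.0918, 86.2%. The loss is 1.1 or 2.4 points.

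**5. Simulation.** Settings: 3,000 runs per scenario, 96 evaluable infants, eight strata (2×2×2), blocks of 2 or 4, linear model. Assumed mixes (diabetic only / SGA only / both / neither) are A = 50/35/10/5% and B = 50/25/15/10%.

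| Mix | Assumed effect of diabetic mother / SGA (points) | Type I error: composite vs separate | Power: composite vs separate |
|---|---|---|---|
| A | 0 / 0 | 4.6% vs 4.7% | 79.6% vs 79.7% |
| A | −15 / −15 | 5.2% vs 5.3% | 80.7% vs 81.0% |
| A | −25 / +10 | 3.9% vs 5.3% | 83.1% vs 85.6% |
| B | 0 / 0 | 4.9% vs 4.9% | 80.7% vs 81.0% |
| B | −15 / −15 | 4.4% vs 4.5% | 82.2% vs 82.3% |
| B | −25 / +10 | 4.1% vs 5.3% | 81.6% vs 83.8% |

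Power differences run from 0.1 to 2.5 points. The largest arise in the steepest scenario, where diabetic-only and SGA-only infants differ by 25 + 10 = 35 points. A second simulation with 95 completers and a 20 to 30 point gap between diabetic and other infants gave 80–83% with the composite and 82–85% with separate terms. At the 30-point gap the test size was about 4.3% versus 5.2%.

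**The case against.** The phrase may be shorthand. It names the same three characteristics that randomisation uses, and an ordinary reader could take it to mean that the models adjust for the stratification factors, or for a four-level class variable. How covariates are coded is also something an SAP normally settles. Both arguments carry weight, and they are why the point is minor. They do not remove it: the protocol itself fixes the covariate set, as one singular condition, in terms that differ from its own randomisation section.

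A reader might infer something stronger: that randomised infants will drop out of the adjusted model and power will fall below 80%. The document does not support that. It needs the diabetic-versus-SGA coding, which the intention-to-treat sentence in the same section argues against. The unadjusted model would lose no infant through covariate coding in any case. Nor can the loss be sized, because Table 1 has no SGA row and no overlap between risk groups.

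Two further inferences also fail. No infant lacks a cell in the stratification scheme, because one eligible only by weight falls in the no/no cell. And no scenario shows type I error inflated by the composite; the test is, if anything, conservative.

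Finally, the efficiency loss depends on an assumed gap in 4-month feeding rates between strata. Section 1.10 reports supplementation rates, not feeding rates, so the document neither confirms nor rules out such a gap. With no gap the loss is nil.

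**Conclusion.** The mismatch between sections 1.6.4 and 1.9.1 is real, and its consequence is small. Under the either-condition reading, the adjusted comparison keeps every infant and stays valid. It gives up about 0 to 3 points of power and tests at about 4% instead of 5%, conditional on an assumed 20 to 30 point difference in feeding rates between strata and on assumed risk-group shares. Under the diabetic-versus-SGA reading, infants with both conditions, or with only a low weight, have no level. That would contradict the section's own intention-to-treat rule, but no figure can be attached to it. The stated 47 and 56 per arm and the 80% power are unaffected. This is a clarification worth making because it is nearly free, not an error that threatens the primary result.

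**What to change.** In section 1.9.1, replace the adjustment sentence with:

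*Adjusted models include the stratification factors as randomised, as separate terms: diabetic mother (yes/no), SGA (yes/no) and sex.*

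In section 1.9.3, define the subgroups by the same three factors, so that infants with both conditions or neither have a stated place. The Bonferroni count should then be based on three factors, not two. If an SAP already codes the terms this way, the protocol sentence only needs to be brought into line with it.

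Cost: one sentence in 1.9.1 and a matching edit in 1.9.3, one extra model degree of freedom and a slightly stricter subgroup threshold. No new data are needed, the sample size does not change, and no infant is lost through covariate coding.
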